Using a randomized cross-over design, in the luteal phase of their menstrual cycles, PMDD women will receive either 1) one night of LWT (sleep 21:00-01:00 h, followed by wakefulness) plus 7 days of AM BWL (light-emitting diode-LED administered for 60 minutes, starting within 30 minutes of habitual wake time) or 2) EWT (wakefulness until 03:00 h, then sleep 03:00-07:00 h) plus 7 nights of PM BWL (administered 90 minutes before habitual sleep onset, for 60 minutes). Following this first intervention, patients will undergo one washout month with no intervention. The second intervention will be completed in the luteal phase of the following month and will be the treatment opposite the one previously performed. Total study duration, including evaluations and washout, will be 5 months (see Figure 1, Section 3, for detailed study flow diagram).

Sample Size and Population

In order to achieve the targeted enrollment goal of 40 completed subjects allowing for a 20% drop-out rate, 48 PMDD women ages 18-45 will be recruited to participate in the study.

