9.2 Sample Size and Randomization

For our primary outcome measures of mood, based on our earlier data reflecting

seven days of light exposure alone² (i.e., without the ‘priming’ effect of wake therapy), we predict the following changes in mood in PMDD subjects (N = 40) after Late Wake Therapy plus AM Light vs. Early Wake Therapy plus PM Light: A significantly greater improvement (decrease in raw score) will be detected at the p = .05 level with (a) 71% power in Hamilton Rating Scale for Depression (HRSD) Score (Mean difference 3.15±9; effect size = .324); (b) > 99% power in atypical score (Mean difference 4.45±5; effect size = .78); (c) > 99 % power in Structured Interview Guide for the Hamilton Depression Rating Scale, Seasonal Affective Disorders (SIGH-SAD) Items (Mean difference 7.0±11; effect size = .627); (d) 86% power in Beck Depression Inventory (BDI) score (Mean difference 6.30±15; effect size = .378).

For the recovery criterion of $\geq 50\%$ decrease from baseline (Chi Square analyses): (a) 97% power for HRSD score (difference in proportions: .44); (b) 70% power for atypical score (difference in proportions: .30); (c) 86% for SIGH-SAD score (difference in proportions: .325); and (d) 93% power for BDI score (difference in proportions: .40). For the remission criterion of reduction to a score of ≤ 8 (Chi Square analyses): (a) 89% power for the SIGH-SAD score; (b) 44% power for the BDI score. All tests are two-tailed.

We also performed power analyses for the primary hypotheses, incorporating the longitudinal nature of the design for the proposed Random Regression model (also known as Multilevel Models, or Growth Curve Models). Procedures describes by Hedeker et al.⁶⁹ for Random Regression Models, with the above data, was used for the proposed study to estimated needed sample size. We assume a Type-I error level (alpha-level) of 0.05, drop-out rate of 10% to 15% and an autoregressive covariance structure, with correlation between sequential assessments set at 0.45 (based on our previous data). We are confident based on our results from these two separate approaches that the proposed study will have minimum power of 80% to yield a statistically significant result for a medium effect size. Here, medium effect size is defined as a treatment difference increasing linearly from 0 at baseline to .5 SD units at the last time point. Type 1 error will be controlled by correcting the p-value per domain.

Treatment Assignment Procedures

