Specifically, data for hypothesis 1.A. will be analyzed using a Random Regression Model (RRM), a generalized linear model described by Gibbons et al.,⁷⁴ Hedeker et al.⁶⁹ and Laird.⁷⁵ The random effects method has several advantages over more traditional analytic approaches such as a change score, end-point or repeated measures analysis of variance. This method allows the inclusion of subjects with missing data or those who were terminated early in the study, without relying on data imputation procedures. This method provides an estimate of the individual variability around the population trend, the variability of the individual intercepts (baseline values) and slopes (changes across time), and the correlation between them. A fully saturated treatment by time model will be utilized for inference. Co-variance structure will be chosen based on Akaike's Information Criterion (AIC). Random treatment effects also will be evaluated for importance based on the model AIC. This plan allows for any group level effects to be incorporated into the model. Denominator degrees of freedom will be calculated using the Kenward-Roger small sample correction. All subjects will be included in the analyses, and we will not focus only on subjects who complete the study. Our methods for data analyses include all subjects with any valid data points in the analyses. Secondary analyses will be performed on data from completers. Type 1 error will be controlled by correcting the p-value per domain. For hypothesis 1.B, an individual's slope for each of the dependent variables listed above will be calculated and will be used for correlational analysis using the Pearson method. In addition, we will examine the number of responders. The operational definition of the criteria for

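### The 80% power given as a minimum for the random regression model is not secured by the plan's stated inputs: it depends on readings that section 9.2 does not state, and on an uncorrected alpha

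*Combined protocol and SAP*

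**What the plan says.** Section 9.2 (Sample Size and Randomization) gives two sets of power figures. The second is for the random regression model. It uses alpha 0.05 and a "drop-out rate of 10% to 15% and an autoregressive covariance structure, with correlation between sequential assessments set at 0.45". The effect is defined as "a treatment difference increasing linearly from 0 at baseline to .5 SD units at the last time point". From this the section concludes that "the proposed study will have minimum power of 80% to yield a statistically significant result for a medium effect size".

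Other parts of the plan bear on the figure:

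- **Section 6.2.4** schedules four HRSD and BDI ratings in each treatment month (3 and 5): the day of the LH surge (LHS), LHS+1, LHS+2 and LHS+8–9. Daily mood ratings (DMR) run from LHS+0 to LHS+10.
- **Section 6.2.5** adds one rating in washout Month 4.
- **Section 9.5.1** defines the primary mood outcome as change from the Month 2 baseline to post-intervention in Months 3 and 5.
- **Section 9.6** plans a saturated treatment-by-time model with random effects and the covariance structure chosen by AIC. It says that "Type 1 error will be controlled by correcting the p-value per domain", as section 9.2 also does.
- **The Précis** (Sample Size and Population) has a "targeted enrollment goal of 40 completed subjects allowing for a 20% drop-out rate, 48 PMDD women ages 18-45 will be recruited".

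**The concern.** A minimum should hold on any fair reading of the inputs. Section 9.2 leaves out the number of assessments, the contrast tested, which SD the 0.5 refers to, the correlation between the two treatment months, and the number of tests per domain.

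The between-month correlation matters most. A crossover gains power when a woman's two treatment results are well correlated. If an autoregressive chain runs through every scheduled rating, her two post-treatment scores are four or five steps apart. Their correlation is then 0.45⁴ = 0.04 or 0.45⁵ = 0.02, and the within-woman gain nearly disappears.

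This is the general power statement behind a sample of 40. If it is too high, a null HRSD or BDI result will be read as stronger evidence against a 0.5 SD effect than the trial can give.

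**Working it through.** **Inputs.** From section 9.2: 40 women, two-sided 0.05, r = 0.45, effect 0.5 SD. Dropout of 10% or 15% leaves 40 × 0.90 = 36 or 40 × 0.85 = 34. The rating schedule is from section 6.2.4.

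**Step 1. Can 80% be reproduced?** Yes, if 0.45 is the correlation between the two post-treatment scores.

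- *Paired comparison.* The standardised difference is 0.5/√(2 × (1 − 0.45)) = 0.477. Noncentral-t power is 84% at 40, 79% at 36 and 77% at 34.
- *Three adjacent assessments (baseline, post 1, post 2), generalised least squares.* Let x be the treatment code (±½) times the share of the effect reached at each assessment. Information per woman is i = [(1 + r²)Σx² − r²(x²_first + x²_last) − 2rΣx_j x_(j+1)]/(1 − r²). Then SE = 1/√(N·i), and power = Φ(0.5/SE − z). With x = (0, ½, −½), i = (0.6013 − 0.0506 + 0.2250)/0.7975 = 0.973. At 40, SE = 0.160 and power = Φ(3.12 − 1.96) = 88%. At 34 it is 82%.
- *0.5 in SDs of the paired difference.* 87% at 40 by noncentral t.

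**Step 2. The planned HRSD/BDI schedule.** Take the Month 2 baseline and four ratings in each treatment month, with r = 0.45 per step. For a linear effect by visit order starting at 0, x = ½ × (0; 0, ⅓, ⅔, 1; 0, −⅓, −⅔, −1). Then Σx² = 0.778 and Σx_j x_(j+1) = 0.444, so i = (0.9353 − 0.0506 − 0.4000)/0.7975 = 0.608. At 40, SE = 0.203 and power = Φ(2.47 − 1.96) = 69%. Coding time by day gives 68%.

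| Four ratings per month, alpha 0.05 | N = 40 | N = 36 | N = 34 |
|---|---|---|---|
| Linear, difference 0 at LHS | 68–69% | 64–65% | 61–62% |
| Saturated model, last-visit difference | 65–66% | 61–62% | 58–59% |

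If the starting difference is free, the linear slope has 36–52% power at 40, depending on time coding and on whether the Month 4 rating is used. If Month 4 counts as a step but the Month 4 and baseline values are left out, the two rows at 40 become 64–65% and 62%. With 48 women analysed, the best figure is 77%.

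**Step 3. Sensitivity of the favourable readings.**

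- *Month 4 counted as an assessment between the two post scores.* Their correlation becomes 0.45² = 0.20. Then i = (0.3006 + 0.2500)/0.7975 = 0.690, and power at 40 is 75%.
- *Daily DMR.* With no difference at LHS, power is 86–88% at 40, and 83% if 15% are lost after the first period. With a free start, and Month 4 not used, it is about 40%.
- *A random intercept added, adjacent correlation kept at 0.45 (the variance share is our assumption).* At 40, the linear model by visit order gives 79%, 86% and 93% for shares of 0.2, 0.3 and 0.4. The saturated last-visit contrast gives 72%, 77% and 82%.

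**Step 4. The promised correction.** The plan gives neither the method nor the number of tests, so Bonferroni with two or four tests is our assumption. For the three-assessment reading:

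- Two tests (alpha 0.025): 81% at 40, 74% at 34.
- Four tests (alpha 0.0125): 73% at 40, 65% at 34.

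**The case against.** The strongest reply is that 80% can be reached on a natural reading. Section 9.5.1 frames the primary mood outcome as baseline to post-intervention in Months 3 and 5. If those are the sequential assessments, power at alpha 0.05 is 82–88% for 34 to 40 women. The low figures need a pure autoregressive chain by visit order, which treats a one-day gap and a gap of weeks as the same step. Section 9.6 plans random effects, which would keep some correlation between the two months. The procedure is also credited to a cited method and to earlier data that are not in the documents.

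Much of this stands. It rules out three stronger conclusions that a reader might draw:

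- *That the true power is 60–70%.* That range depends on one covariance assumption and one schedule. Other readings give figures well below and well above it.
- *That 80% is an arithmetic error.* The section omits too many inputs for that to be shown, and Step 1 reproduces 80% or more.
- *That no reading reaches 80% after correction.* The three-assessment reading with 48 complete cases gives 82% at 0.05/4.

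The figures for 34 and 36 also apply only if the 40 in section 9.2 is counted before dropout. The Précis treats 40 as completers, and the mixed model keeps partial data.

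What the reply does not rescue is the word minimum. An effect that grows linearly from baseline to a last time point fits repeated ratings within a treatment month better than one rating per month. Month 4 ratings lie between the two post scores and are listed for analysis in section 9.6. Section 9.2 does not mention a random-intercept share, paired-difference units or the DMR schedule.

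**Conclusion.** The claim does not hold as a minimum. With the stated 0.45 run through the planned HRSD/BDI ratings at two-sided 0.05, power for 0.5 SD is about 65–69% at 40 women, 36–52% with a free starting difference, and at most 77% with 48 analysed. Whether 80% is met depends on choices that section 9.2 leaves unstated. Even the simple paired reading falls just under 80% at 36 and 34. The power statement also ignores the plan's own multiplicity correction, which takes the three-assessment reading to 73% at 40 under an assumed four tests.

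The Step 2 figures rest on autoregressive steps counted by visit order, unit variance at every rating, 0.5 in SDs of a single rating, and a normal approximation. The first set of power figures in section 9.2 (for example 71% for HRSD) concerns other effect sizes, so it cannot confirm the 80%.

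**What to change.** In section 9.2:

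1. Delete the statement of an 80% minimum.
2. Recompute power for the section 9.6 model on the section 6.2.4 schedule, at the per-domain corrected alpha. State the assessments included, the contrast, the SD unit of the 0.5, the correlation between the two treatment months, the number of tests per domain and the correction method.
3. Say whether 40 is before or after dropout, and reconcile the 10–15% here with the 20% in the Précis. There, 48 × 0.80 = 38.4 completers, and 40 completers at 20% loss need 40/0.80 = 50 recruits.
4. Report the resulting power by outcome (HRSD, BDI and DMR have different schedules), or the detectable effect at 80% power.

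The 65–69% given here should not be printed as the definitive replacement, because it too rests on an assumed covariance. The cost is a recalculation and probably a less favourable stated figure. The design does not change.

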Enrollment in the treatment phase occurs during a clinic visit scheduled between cycle days 1 and 10 of the menstrual cycle immediately following successful completion of the evaluation phase (Month 3), provided they are qualified to participate and they sign a Study Consent form. During this visit, they will also be assigned an individual participant identifier (Master Code Number) and be randomized to the first of two treatment conditions. Enrollment ascertainment for the treatment phase and randomization occur at the same time.

Randomization

All subjects for this study will be enrolled in the evaluation phase of the study at the time of the first screening visit when patients sign a Screening Consent form. Enrollment in the treatment phase occurs during a clinic visit scheduled between cycle days 1 and 10 of the menstrual cycle immediately following successful completion of the evaluation phase (Month 3), provided the subject is qualified to participate. During this visit, we will randomize subjects to the first of two treatment conditions. Starting on the day of ovulation, subjects will be randomized to either 1) one night of Late Wake Therapy (LWT: sleep 21:00-01:00 h, followed by wakefulness) plus 7 days of AM Bright White Light (BWL: light-emitting diode-LED administered for 60 minutes, starting within 30 minutes of habitual wake time) or 2) Early Wake Therapy (EWT: wakefulness until 03:00 h, then sleep 03:00-07:00 h) plus 7 nights of PM BWL (administered 90 minutes before habitual sleep onset, for 60 minutes). The problem of randomization imbalance, observed particularly when independent groups (such as group 1 receiving only treatment A and group 2 receiving only treatment B) are used, will be addressed by two processes. First, this study uses a cross-over design and subjects will be assigned to the other treatment in the luteal phase of their next menstrual cycle after a one-month washout period. Second, subjects will be randomized to study treatment group in a 1:1 ratio with variably-sized block design. This randomization will be done using SAS programs that we have used for many of our clinical trial studies. The block sizes are known only to the study statistician. The randomization table will be prepared prior to the initiation of the study.

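### The continuous mood powers and the 80% minimum in 9.2 are computed at alpha .05, but the plan will test the mood scales with p-values corrected per domain

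*Combined protocol and SAP*

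**What the plan says.** Section 9.2 predicts, for 40 women: "A significantly greater improvement (decrease in raw score) will be detected at the p = .05 level with (a) 71% power" for HRSD, then above 99% for the atypical score, above 99% for SIGH-SAD and 86% for BDI. It adds "All tests are two-tailed". For the random regression model it says "We assume a Type-I error level (alpha-level) of 0.05, drop-out rate of 10% to 15% and an autoregressive covariance structure", and concludes that power is at least 80% for a medium effect, defined as a difference that grows from 0 to .5 SD.

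The paragraph then closes with "Type 1 error will be controlled by correcting the p-value per domain". Section 9.6 repeats that sentence where it describes the analysis of hypothesis 1.A, so it is part of the decision rule. Neither section says what the domains are, how many tests each holds or which correction is used. No power is given at a corrected level.

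Three lists could define the mood domain:
- 9.2 powers four scales: HRSD, atypical, SIGH-SAD, BDI.
- Hypothesis 1.A in 9.1 has five measures: SIGH-SAD, BDI, BAI, DMR and the global assessment of effectiveness.
- The primary outcome in 9.5.1 has seven: HRSD, BDI, atypical symptoms from SIGH-SAD, BAI, mania ratings, PGWI and DMR.

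**The concern.** Power belongs to a particular test at a particular level. If several mood scales share one domain and their p-values are corrected, a scale will in general have to clear a stricter threshold than .05, and its power falls below the figure computed at .05. Section 9.2 states the powers for one rule and, a few lines later, commits to another.

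The 80% statement is the plan's assurance that the proposed study is large enough. Anyone who later interprets a non-significant HRSD or BDI result will look back at 71% and 86%, which may overstate the chance that the corrected test had of finding the predicted effect.

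**Working it through.** **1. The plan's own figures.** A paired t-test with n = 40, two-sided .05 and the printed effect sizes (.324, .78, .627, .378) gives HRSD 51.5%, atypical 99.8%, SIGH-SAD 97.2% and BDI 64.5%. The plan prints 71%, >99%, >99% and 86%, so only the atypical figure reproduces. The closest variant tried is a one-sided .05 normal approximation on mean difference divided by SD. For HRSD, 3.15/9 = 0.35 and 0.35 × √40 − 1.645 = 0.569, which gives 71.5%; BDI comes to 84.4%. That conflicts with the two-tailed statement. The 80% cannot be reproduced, because the number of time points and the contrast are not given. No variant tried makes the printed figures those of a stricter, corrected level: a smaller alpha moves HRSD and BDI further below them.

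This reproduction problem is a separate matter. From here the printed powers are taken as true at two-sided .05, which favours the plan.

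**2. Bonferroni over k scales (k and method are assumptions).**
Noncentrality = z(power) + 1.960. New power = Φ(noncentrality − z(1 − .025/k)).

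Noncentralities:
- HRSD: 0.553 + 1.960 = 2.513
- BDI: 1.080 + 1.960 = 3.040
- 80% minimum: 0.842 + 1.960 = 2.802
- Atypical and SIGH-SAD, with 99% assumed for >99%: 2.326 + 1.960 = 4.286

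Critical values are 2.241 (k = 2), 2.498 (k = 4) and 2.690 (k = 7). For HRSD at k = 4, Φ(2.513 − 2.498) = Φ(0.015) = 51%. For the 80% minimum at k = 4, Φ(2.802 − 2.498) = Φ(0.304) = 62%.

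| | at .05 | k = 2 | k = 4 | k = 7 |
|---|---|---|---|---|
| HRSD | 71% | 61% | 51% | 43% |
| BDI | 86% | 79% | 71% | 64% |
| 80% minimum | 80% | 71% | 62% | 54% |
| Atypical, SIGH-SAD | 99% | 98% | 96% | 94% |

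Here k = 4 matches the scales powered in 9.2 and k = 7 the list in 9.5.1; k = 2 is the smallest family that involves any correction. At k = 5, the length of the hypothesis 1.A list, BDI is 68% and the 80% minimum becomes 59%. No HRSD figure is attached to that list, because HRSD does not stand on it as a separate measure.

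**3. Stepwise methods over the four powered scales.** Four normal test statistics were simulated with means 2.513, 4.286, 4.286 and 3.040 and a common correlation between 0 and 0.7.
- Holm: HRSD 68–69%, BDI 81–83%.
- Hochberg: HRSD 69–70%, BDI 82–84%.

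The loss is small because the two scales with near-certain power are usually rejected first, which leaves HRSD and BDI to be tested at laxer levels.

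**4. Fixed sequence.** The first scale in the order keeps .05 in full and loses nothing.

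**The case against.** The strongest reply is that the size of the loss comes from the assumed method, not from the plan. This stands. Under Holm or Hochberg at k = 4, HRSD loses about 1–3 points and BDI about 2–5, against 20 and 15 under Bonferroni. A reader might infer that the corrected test has only even odds for HRSD; that holds only for Bonferroni with about four or five scales in a family that includes HRSD. A reader might also infer that power is overstated as soon as there is more than one scale; a fixed-sequence procedure, which the documents do not rule out, is a counterexample for its first scale.

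It is also tempting to say that every power in 9.2 is affected. The chi-square response and remission powers state no alpha, so they lie outside this point unless those tests belong to the corrected family.

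Further, two of the four scales keep high power under any of these methods, and under Bonferroni at k = 4 the chance that at least one of the four is significant stays near 99%. The 80% sentence promises a significant result, not one on each scale. This limits the harm but does not remove the mismatch: that 80% is explicitly computed at .05, and the plan does not define success as at least one significant scale.

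Finally, nothing in the documents says that a null HRSD or BDI result would be read as evidence against the treatment. That is a risk of interpretation, not a stated rule.

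**Conclusion.** The point holds for the four continuous mood powers and for the random regression minimum of 80%. They are stated at .05, while 9.2 and 9.6 commit to a corrected p-value in a domain with several scales, and no list in the plan reduces that domain to one.

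The mismatch is certain; its size is not. It runs from nothing for the first scale of a fixed sequence, through a few points under Holm or Hochberg, to the Bonferroni losses in the table. All these figures assume that the printed powers are correct at two-sided .05. Because the HRSD and BDI powers do not reproduce at that level, the adjusted figures for them are probably optimistic and serve as illustrations, not as replacement text.

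A reader might conclude that 40 women are too few. The documents do not support a specific larger number, since they fix neither the family nor the method.

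**What to change.** In 9.2 and 9.6, name the scales that make up the mood domain and the correction method. This has to come first, because 9.6 at present gives no corrected level at which power could be computed. A stepwise method such as Holm is a sensible choice: it keeps family-wise error control whatever the correlation between scales and, on the plan's own figures, costs far less power than Bonferroni. Then restate the continuous and random regression powers under that procedure, and replace the 80% minimum by the figure that results. Say also whether the response and remission tests belong to the corrected family.

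Alternatively, name one primary mood scale tested at .05 and state power for that scale only.

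Neither route changes enrolment or study procedures. The cost is a revised paragraph, probably with less favourable figures.
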